5.8.1 Main analytical approach.....	22
5.8.2 Sensitivity Analyses.....	26
5.8.3 Handling of missing data or dropouts.....	27
5.9 Exploratory Analyses.....	28
5.10 Safety Analyses.....	28
5.10.1.1 Extent of Exposure.....	29
5.10.1.2 Adverse Events	29
5.11 Protocol Violations	30
5.12 Other Analyses.....	30
5.13 Interim Analyses	31
5.14 Changes to Protocol-Planned Analyses	31
6. Supporting Documentation.....	32
6.1 Appendix 1: Definitions and Medical Codes.....	32
6.2 Appendix 2: CRF forms or questionnaires	35
6.3 Appendix 3: Mock TFLs.....	39

CONFIDENTIAL

[Protocol number: UHG (J2X-NS-I002)] SAP [v.3]

7. **References.....50**

Table of Abbreviations

LY3819253

CONFIDENTIAL

[Protocol number: UHG (J2X-NS-I002)] SAP [\[v.3\]](#)

1. Revision History

This is the third version of statistical analysis plan (SAP) for the UNITED protocol. We (UHG) update the second version according to the feedback from Eli Lilly.

LY3819253

2. Background and Rationale

The severe acute respiratory syndrome coronavirus 2 (SARS-CoV-2) has resulted in the pandemic spread of coronavirus disease 2019 (COVID-19), which in critical cases results in progressive pulmonary failure, complications with acute respiratory distress syndrome (ARDS), and in some cases death. There is an urgent need for effective therapeutics to modify disease outcomes. Bamlanivimab (LY3819253) is a neutralizing IgG1 monoclonal antibody (mAb) to the spike protein of SARS-CoV-2. It is designed to block viral attachment and entry into human cells, thus neutralizing the virus, potentially preventing and treating COVID-19.

This is an open-label, pragmatic, single-arm observational study of Bamlanivimab (LY3819253) infusion efficacy and safety using matched, real-world, external controls in participants with mild to moderate COVID-19.

3. Objectives

The purpose of this study is to: Determine whether symptomatic high risk COVID-19 participants will have a reduction in hospitalizations compared to a real-world external control population when provided with a combination of symptom tracking and single dose administration of Bamlanivimab (LY3819253) via an at-home infusion visit.

3.1 Primary Objective

The primary objective is related to efficacy and is:

- To determine the incidence of COVID-related hospitalization at Day 28 among Bamlanivimab-treated relative to external controls.

3.2 Exploratory Objectives

The exploratory objective is related to efficacy and is:

- To determine the incidence of COVID-related mortality at Day 28 among Bamlanivimab-treated patients relative to external controls.

3.3 Safety Objectives

The safety objectives are considered as secondary objectives. They are:

- To describe the incidence of infusion reactions during receipt of infusion and during the defined infusion follow-up period (follow-up period to be consistent with EUA fact sheet for healthcare providers),
- To describe the incidence of patient reported adverse event (AE) outcomes through Day 28.

4. Research Design

4.1 Summary of Research Design

This is an open-label, pragmatic, single-arm observational study using matched, real-world, external controls in participants with mild to moderate COVID-19. Potential participants will track for symptom development while at home and upon reporting of symptoms will be tested for COVID-19. If positive for COVID-19, a one-time at-home infusion of 700mg Bamlanivimab (LY3819253) will be provided by Optum Infusion. Study participants who received infusion will then be tracked for 28 days to assess for any additional medical care needed or if hospitalization was required.

There is no placebo arm in the study, hence, we will identify external matched controls using propensity score matching and assess the robustness of findings via sensitivity analysis. We elaborate how we collect data from the target population and what data elements will be captured in the following subsections. Figure 2 (in Section 4.4) describes how we identify study participants and Figure 3 (in Section 4.5) illustrates the timeline of study participants and controls.

4.2 Data Collection

The data sources for study participants and the pool of potential controls are not all the same because we don't enroll matched controls in this study. To make sure both groups are symptomatic, we will use Optum electronic medical record (EMR) data to select symptomatic COVID-19 cases as candidates of control, while this information for study participants comes from ProtectWell symptoms data. We summarize the data sources for study participants and matched controls in Table 1.

For enrolled participants, tracked data collection begins from first report of symptoms via ProtectWell. The data collection timepoints are:

1. First report of symptoms
2. COVID-19 test result (positive – moves forward; negative – resets the experience)
3. Date of receipt of Bamlanivimab (LY3819253) via infusion (Day 1)
4. Day 1 infusion (pre, during, post) collection of CRF data (participant vitals/health information and any events experienced)
5. Day 1 post-infusion baseline wellness check through Day 28 final wellness check
6. Any point during Day 1 post-infusion baseline through Day 28 where wellness check indicates participant is feeling worse
7. Point from participant marking feeling worse through action taken (live daily check-in via clinical support, recommendation to seek medical care and/or requiring hospitalization)

Regarding the timeline, the overall duration for enrolled participants is up to 6 months with symptom tracking only. Once an enrolled participant becomes a study participant after reporting symptoms, it is up to 38 days (28 days of active participation after receipt of infusion on Day 1 and up to 10 days from report of symptoms to receive infusion). For matched controls, the active insurance coverage after date of symptoms onset should be up to 38 days. We require matched controls to remain enrolled in utilized data sources to assure data availability. Similar to enrolled participants, matched controls may die after the synthetic date of treatment.

Commented [WWY1]: Would suggest to add A figure to illustrate study design, including screening and treatment time point and assessment period

Commented [JAT2R1]: Thanks for the suggestion. I added a sentence directing the audience to Figures 2 and 3 on the screening process and timeline.

Table 1. Main data sources of study participants and the potential pool of controls.

Study population	Data name	Data description
Study participants	Optum infusion pharmacy data	Day 1 at-home infusion will collect vitals and other essential data pre, during and post-infusion using an established case report form (CRF) to collect any events experienced during and post-infusion related to Bamlanivimab (LY3819253)
	ProtectWell data	during symptom tracking – status of what was selected per daily check-in, first trigger point of noting experiencing symptoms, if COVID-19 positive and received infusion – Day 1-28 wellness tracking (in numeric 1-10 ratings)
	UHC claims data (UHC members only)	data including demographic characteristics (e.g., age, gender, race) and existing comorbidities (e.g., congestive heart failure, diabetes, chronic kidney disease)
	Blended Census Reporting Tool (BCRT) data (UHC members only)	real-time inpatient admission data including ICD-10 diagnosis codes, discharge status, COVID test status reviewed by UHC's clinical team; will be used as complementary to Optum infusion pharmacy data for COVID hospitalizations
	Clinical Data Services Management (CDSM) data (UHC members only)	SARS-CoV-2 lab testing data from reporting health systems, clinics, and third-party labs; will be used as complementary to Optum infusion pharmacy data for COVID tests
Potential pool of controls	Optum EMR data	primary source to confirm for presence of symptoms during COVID+ test of a matched individual (analogous to the symptoms collected as part of ProtectWell data for study participants); will also be used for COVID test status and COVID hospitalization of all potential controls, and for demographic characteristics, existing comorbidities, COVID test status and COVID hospitalization of potential non-UHC controls.
	UHC claims data (UHC members only)	data including demographic characteristics (e.g., age, gender, race) and existing comorbidities (e.g., congestive heart failure, diabetes, chronic kidney disease)
	Blended Census Reporting Tool (BCRT) data	real-time inpatient admission data including ICD-10 diagnosis codes, discharge status, COVID test

LY3819253

(UHC members only)	status reviewed by UHC's clinical team; this dataset does not include symptom information during COVID test, hence it will be only used as a potential sensitivity analysis data source
Clinical Data Services Management (CDSM) data (UHC members only)	SARS-CoV-2 lab testing data from reporting health systems, clinics, and third-party labs; this dataset does not include symptom information during COVID test, hence it will be only used as a potential sensitivity analysis data source

4.3 Sample Size Determination

[figure not shown]
To evaluate treatment effects based on the discrete clinical endpoint (hospitalization rate at Day 28 post infusion), we compared the proportion of events (i.e., prevalence rate or COVID hospitalization rate) between treatment and matched-control group which is our primary objective of interest. Specifically, we are interested in testing the efficacy (superiority) of treatment effects, which can be written formally in one- or two-sided hypotheses. Assume the null hypothesis is two-sided. We performed the power analyses based on a 5% level of significance (Type-I error) for a set of values of power (i.e., 0.75, 0.80, 0.85, 0.90, 0.95). We obtained the minimally required sample size for multiple scenarios - (a) hospitalization rate (0.20, 0.25, 0.30, 0.35) based on BCRT and CDSM data (b) different possible efficacy rates (reduction rates in hospitalization after using treatment). We used multiple methods - (i) a two-sample proportion test in detecting a difference between two binomial probabilities (Casagrande, 1978) (Fleiss, 1980) and (ii) McNemar's test (Agresti, 2003).

The former test statistic follows Gaussian distribution asymptotically exploiting large sample theory and the latter is designed to test categorical shift (or association) in responses (hospitalization rate in our example) between treatment and control group where the idea is to cast the data into a 2 x 2 contingency table. While both these methods provide competitive and comparable results, reported below are the results based on the first method, a two-sample proportion test with continuity correction. The one-sided hypothesis requires a smaller sample size than that of a two-sided test.

Figure 1 illustrates the sample size required with a case and control ratio being 1:1 for different hypothetical scenarios. As expected, when the true prevalence rates between treatment and control groups are small, it requires a larger sample size to detect a statistically significant difference. As reported in the Lilly SARS-CoV-2 Neutralizing Antibody Program Update, the hospitalization rate for the treatment (i.e., LY-CoV555 Mono) group drops by 75% compared to that of the placebo group. Based on this relative change, we will need a total sample size less than 1,000; follow the power curves (i.e., corresponding to 0.10 Type-II error) in Figure 1 top-right panel with 75% (approximately) reduction rate. For example, using the COVID hospitalization rate of 25%, reported below in Table 2, are the minimum COVID diagnosed patients required to detect varying differences between the proportions at a 5% level of significance with 90% power of rejecting a two-sided null hypothesis.

Table 2. A case study for baseline hospitalization rate of 25%.

Absolute differences (assumed) between prevalence rates of treatment and control group (% reduction from baseline rate)	Total sample size (treatment and control as 1:1)
0.24 (95%)	97
0.21 (85%)	129
0.19 (75%)	175
0.16 (65%)	244
0.14 (55%)	355
0.11 (45%)	550
0.09 (35%)	940
0.06 (25%)	1,899
0.04 (15%)	5,416
0.01 (5%)	49,900

[figure not shown]

Figure 1. Power analyses at 5% level of significance for six scenarios with baseline COVID hospitalization rates of 15% (top-left), 20% (top-right), 25% (middle-left), 30% (middle-right), 35% (bottom-left), and 40% (bottom-right) based on CDSM and BCRT databases. Varying prevalence rates along with reduction (in parenthesis) in hospitalization from baseline (i.e., control group) for the treatment group are considered (X-axis) as 95% to 5%. Reference lines corresponding to 5,000 and 2,000 sample size are drawn for convenience of comparison.

4.4 Study Population

4.4.1 Selection Criteria

Both study participants and matched controls will meet the inclusion and exclusion criteria below.

Inclusion Criteria:

- Age 65+, confirmed SARS-CoV-2 positive, located in an area where Bamlanivimab (LY3819253) is available for infusion
- Have mild or moderate COVID-19 symptoms (after stage 1 of symptom tracking)

Commented [JAT4]: Update to keep the same criteria in the latest protocol (version 10 on Feb 3, 2021).

Commented [JAT5]: Remove it as it is no necessary for active participants and controls.

- Control only: Confirmed symptomatic COVID-19 through Optum EMR data.

Exclusion Criteria:

- Current (from first symptom report) hospitalization for COVID-19
- Prior administration of Bamlanivimab

Commented [JAT6]: Remove as not necessary per the EUA.

4.4.2 Patient Groups

Before analysis there are two study populations – study participants and the pool of potential controls. For study participants, we plan to enroll aged 65 and older, who are deemed high risk per the emergency use authorization, if contracting COVID-19. For the pool of potential controls, we plan to utilize UHC members who have Optum EMR data to confirm presence of symptoms during COVID test as well as having continuous enrollment to access to their claims and prospective hospitalization and death data. If applicable, non-UHC members or UHC members who did not seek care at OptumCare facilities may be used as members of the control population based on EMR review and matching to enrolled participants.

During analysis (i.e., after matching), there will be two study populations – study participants after matching and matched controls. Note that the size of study participants after matching may be smaller than the size of original study participants if a matched control can't be identified.

The targeted number of enrolled participants for tracking for symptoms is 500,000, and the targeted number of study participants who are COVID-19 positive and consent to receive Bamlanivimab (LY3819253) is 7,500. Figure 2 illustrates the process to identify study participants. Regarding controls, we set the case:control ratio at 1:1 and plan to identify 7,500 matched controls which is the same as number targeted for study participants.

Given the current enrollment speed (as of March 9, 2021) and the decreasing COVID-19 hospitalization rate across the US, we may not achieve the target number of study participants, 7,500. However, according to the power analysis in Section 4.3, it is sufficient to have 1,000 study participants with another 1,000 matched controls to detect a 33% decrease in the hospitalization rate (i.e., from 15% to 10%) with power 0.8 and level 0.05.

Commented [JAT7]: Remove as treatment is allowed in this situation per the EUA.

Commented [JAT8]: Remove prior vaccination from exclusion criteria as this is not required per the EUA.

Commented [WWY9]: Should we replace continuous member enrollment?

Commented [WWY10]: Given current enrollment speed, it will be helpful to show what is the minimal sample size for Bam treated group required for the primary objective analysis.

Commented [WWY11]: Suggest to provide power estimate and assumptions (e.g. distribution, COVID-19 hospitalization rate for both treatment groups, and match rate...)

How many controls are targeted before the matching? Would suggest to have sample size with the ratio of 1:3 between treated vs controls.

Commented [JAT12R11]: Added the power analysis from the protocol as a new section above (sec 4.3 sample size determination).

Commented [WWY13]: Suggest to have a separate section of sample size.

[figure not shown]

Figure 2. Flow chart of the process of identifying study participants.

4.5 Endpoints

The following definitions of endpoints hold for all analyses described in this statistical analysis plan. For study participants, we define the study endpoint as 28 days after date of the Bamlanivimab infusion. This holds for both outcomes of COVID-related hospitalization with or without time consideration (i.e., no censoring vs censoring at Day 28). For example, if a study participant hasn't been hospitalized due to COVID-19 within 28 days after COVID-19 diagnosis, we'll treat the binary response of COVID-19 hospitalization as 0 without time consideration. However, with time consideration, it becomes right-censored since this participant may be hospitalized 29 or more days after COVID-19 diagnosis and our observation period is 28 days after COVID-19 diagnosis. More details are described in Section 5.8.1.3. For the pool of potential controls, we define the study endpoint as 28 days after a synthetic date of treatment. We will randomly select a number from the distribution of number of days after date of symptoms onset in study participants to identify an index date with which to define 28 days post infusion where we will monitor claims and EMR data for hospitalizations and mortality.

Commented [WWY14]: Should be the pool of controls which was before PS matching.

Figure 3 illustrates the timeline for study participants and controls to ensure alignment on an index date for symptoms onset and the follow-up period. Since the control group will not have an infusion date associated with them, we will randomly select a number from the distribution of number of days after date of symptoms onset in study participants to identify an index date with which to define 28 days post infusion where we will monitor claims and EMR data for hospitalizations and mortality.

[figure not shown]

Figure 3. Illustration of the timeline for study participants and controls.

For patients who do not experience a COVID-19 related hospitalization by Day 28 following the date of infusion or synthetic treatment, a censoring date is defined as the earliest of 28 days following the date of treatment, or for study participants, the early discontinuation date due to lost to follow-up.

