5.4 Participant Dispositions – Study Participants Group Only

The number and percentage of study participants who complete the study or discontinue early will be tabulated by 28 days. Here, we consider that the subset of study participants for whom outcome data can be obtained through UHC claims, Optum EMR, or Optum infusion pharmacy data sources during the 28 days post-infusion time period are completing the study, whereas remaining subset of study participants for whom outcome data cannot be confirmed by any of these data sources during the 28 days post-infusion time period are discontinuing early. All patients who enter the study and discontinued from the study will be listed, and if available, the timing (from receiving study treatment) and reason of discontinuing the study will be reported.

Commented [XM24]: The number and percentage of study participants who complete the study or discontinue early will be tabulated by 28 days. Reasons for discontinuation will be summarized.

All patients who enter the study and discontinued from the study will be listed, and the timing of discontinuing (from receiving study treatment) the study will be reported. If known, a reason for their discontinuation will be given.

In addition, a graphical summary (i.e., KM plot) of time from study treatment to early permanent discontinuation of study due to AEs may be generated if there are a substantial number of such events.

Commented [XM25]: Please add sections:

- Multiple Comparisons/Multiplicity
- Patient Characteristics
- Prior Medication and Concomitant Therapy
- Protocol Violations

Commented [WWY26R25]: Refer to attached sample SAP

Commented [JAT27R26]: Added the new section 5.7.

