5.8.3 Handling of missing data or dropouts

Other potential sources of bias are missing data, selection bias, and measurement error. We perform the analyses under the assumption of missing (completely) at random. We exclude the cases with missing features if the number of missing subjects is less than 5% of total sample size. Otherwise, we impute values using multivariate imputation by chained equations (MICE) algorithm (Van Buuren, 2018).

The effect of selection bias will be attenuated by appropriately selecting control subjects (who to be matched to treated) from a large pool of patients who are clinically COVID symptomatic.

Systematic bias arising from socio-economic factors will be mitigated by adjusting for various demographic, economic, and societal variables. Measurement errors if there are any, would be considered as random noises, and will be negligible.

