Table A8. Standardized difference in mean and variance ratio of the propensity score and all matching covariates before propensity score matching

Commented [XM58]: Would report both results before and after match

Variable	Standardized difference in mean	Variance ratio
Propensity score		
Age (continuous or categorical):		
65-		
65 – 69		
70 – 74		
75 – 79		
80+*		
*: We can separate 80+ into finer groups as needed.		
Gender		
Race:		
White		
Black		

LY3819253

CONFIDENTIAL

[Protocol number: UHG (J2X-NS-I002)] SAP [\[v.3\]](#)

Asian	
Hispanic	
Other	
Urbanization of residence:	
Urban	
Suburban	
Rural	
Socioeconomic index	
Dual status	
With Medicaid	
Elixhauser comorbidity score	
Elixhauser conditions [*]	
[*] : There are 29 conditions in total as shown in Table A1.	
Immunosuppressive treatment 6 months prior to date of COVID diagnosis	

Dataset: dataset location (data table name with the corresponding database in Google BigQuery)

Program: program location/program name.R

Output: output location/output name.csv or .xlsx

Repeat Table A8:

Table A8.2

Standardized difference in means and variance ratio of the propensity score and all matching covariates after propensity score matching

Propensity score matched population

Programming notes:

Replace “before propensity score matching” with “after propensity score matching” in the table title.

LY3819253

CONFIDENTIAL

[Protocol number: UHG (J2X-NS-I002) SAP [v.3]

Table A9. Unadjusted and adjusted measures of COVID-19 hospitalization risk in study participants and matched controls.

Outcome	Results (e.g., 95% CI and p-value)
Rate of COVID-19 hospitalization w/o considering censoring on Day 28 (i.e. binary endpoint) among study participants vs matched controls	
Adjusted odds ratio w/o considering censoring on Day 28 (i.e. binary endpoint) among study participants vs matched controls	
Adjusted hazard ratio with considering censoring on Day 28 among study participants vs matched controls	

Commented [XM59]: Would include 95% CI and p value.

Commented [XM60]: Not sure what this mean?

Commented [JAT61R60]: This means a binary response. If we don't observe a covid-19 hospitalization for a patient within 28 days after his/her treatment, we define this response as 0, instead of censoring on Day 28.

Dataset: dataset location (data table name with the corresponding database in Google BigQuery)

Program: program location/program name.R

Output: output location/output name.csv or .xlsx

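### The SAP has no rule for unconfirmed outcomes in the binary primary endpoint, so by default a treated participant of unknown status counts as not hospitalized

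*SAP*

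**What the plan says.** The primary endpoint is COVID-related hospitalization at Day 28 as a binary variable, compared in matched pairs by McNemar's test at 0.05 (SAP 5.8.1.3).

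- **Coding.** SAP 4.5 takes a participant who was not admitted in the window and will "treat the binary response of COVID-19 hospitalization as 0 without time consideration". The author's comment on mock Table A9 (SAP 6.3) explains the binary row: where the study does not "observe a covid-19 hospitalization for a patient within 28 days after his/her treatment, we define this response as 0", rather than censoring at Day 28.
- **Unconfirmed participants.** SAP 5.4 says that participants "for whom outcome data cannot be confirmed by any of these data sources during the 28 days post-infusion time period are discontinuing early". The closing paragraph of 4.5 gives participants lost to follow-up a censoring date. That date has a use only in the time-to-event analysis.
- **Missing data.** SAP 5.8.3 begins its rule with "We exclude the cases with missing features", applied below 5% missing, with multiple imputation by chained equations otherwise. It does not name the outcome.
- **Controls.** SAP 4.2 states "We require matched controls to remain enrolled in utilized data sources to assure data availability". No equivalent requirement is stated for participants.
- **Sources.** SAP 5.8.1.3 finds admissions in the treated group through infusion pharmacy and BCRT data, and in controls through UHC claims and Optum EMR. SAP Table 1 limits BCRT to UHC members.
- **Who is analysed.** SAP 5.1.1 says all analysis populations are UHC members. SAP 5.8.1.2 says the treated group has UHC and non-UHC members and describes how the latter will be matched.

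**The concern.** The plan names a group with unknown outcome and then defines its primary endpoint without saying what happens to that group. The only operational wording turns on whether an admission was observed, not on whether its absence was confirmed. An analyst who follows it would enter 0 for a participant admitted to a hospital outside the data feeds, or for one who stopped responding because of an admission. Once that 0 is entered nothing is missing, so the rule in 5.8.3 would not clearly be triggered.

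The follow-up requirement is stated for one group only, and the outcome sources differ between groups. A gap in capture on the treated side therefore need not be matched on the control side. The comparison could show a lower treated rate that reflects missing records rather than the drug.

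**Working it through.** **1. The plan's own figure.** Inputs from SAP 4.3: "A case study for baseline hospitalization rate of 25"%, "at a 5% level of significance with 90% power of rejecting a two-sided null hypothesis", using "a two-sample proportion test with continuity correction". For the 75% reduction row, p1 = 0.25, p2 = 0.0625, D = 0.1875, mean 0.15625.

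- Uncorrected n per group = [1.960·√(2·0.15625·0.84375) + 1.2816·√(0.25·0.75 + 0.0625·0.9375)]² / 0.1875² = 76.71.
- Corrected n = (76.71/4)·[1 + √(1 + 4/(76.71·0.1875))]² = 87.05.
- Total = 174.1, rounded up to 175, as stated.

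All ten rows of Table 2 reproduce this way, so the two-proportion calculation is a sound base for what follows.

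**2. Inputs for the bias check.** From SAP 4.4.2: 1,000 per group, rates of 15% and 10%, power 0.8, and a full target of 7,500 per group. The unconfirmed share d of participants appears nowhere in the documents; I assume 2% to 20%.

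**3. Unconfirmed coded 0, no drug effect, complete control capture, equal risk.** The apparent treated rate is 0.15(1 − d). The chance of a significant result favouring the drug is Φ[(pC − pT − 1.96·se0)/se1], where se0 is the pooled and se1 the unpooled standard error.

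At d = 10% and 1,000 pairs: pT = 0.135, se0 = √(2·0.1425·0.8575/1000) = 0.01563, se1 = √((0.1275 + 0.1168)/1000) = 0.01563. Then (0.015 − 0.03064)/0.01563 = −1.00, which gives 0.158.

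| d | Treated vs control | Rate ratio | False pro-drug result, 1,000 pairs | 7,500 pairs |
|---|---|---|---|---|
| 2% | 14.7% vs 15% | 0.98 | 0.038 | 0.074 |
| 5% | 14.25% vs 15% | 0.95 | 0.069 | 0.255 |
| 10% | 13.5% vs 15% | 0.90 | 0.158 | 0.748 |
| 20% | 12% vs 15% | 0.80 | 0.501 | >0.999 |

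The nominal value is 0.025. Simulating the planned McNemar test with independent pairs gives the same figures to within 0.001.

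**4. Higher risk among the unconfirmed.** If they have k times the risk of the others and the overall rate is 15%, the null ratio is (1 − d)/((1 − d) + k·d). With k = 2 it is 0.905, 0.818 and 0.667 at d = 5%, 10% and 20%. The last equals the whole 15% to 10% effect in SAP 4.4.2.

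**5. Incomplete control capture.** If a share s of control admissions is captured, the null ratio is (1 − d)/s. With d = 10% and s = 90% it is 1.00. With d = 5% and s = 90% it is 1.06, against the drug.

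**6. Dropping unconfirmed pairs.** With equal risk the treated rate is unbiased. Power for 15% versus 10% from 1,000 pairs falls from 0.923 to 0.910, 0.894 and 0.857 when 5%, 10% and 20% are lost. With k = 2 some bias remains: the ratio among confirmed participants is 1/((1 − d) + 2d), or 0.95, 0.91 and 0.83 at 5%, 10% and 20%.

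**The case against.** The strongest reply is that the plan never says unconfirmed participants are coded 0. The sentence in 4.5 concerns someone who was not hospitalized, and it contrasts a binary 0 with administrative censoring at Day 28. The Table A9 text is a margin reply about that same contrast, and its wording covers patients in either group. SAP 5.8.3 has dropouts in its title and could be read as excluding or imputing them. This stands in part: the coding is the default that follows from the wording, not a declared rule for this group. It does not settle the matter, because 5.8.3 speaks of features and nothing sends an unobserved admission to it.

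A reader might also infer that controls have complete outcomes, so that the error can only favour the drug. The documents do not support that. SAP 4.2 requires enrollment, not a confirmed outcome. SAP 4.4.2 allows non-UHC controls, and UHC members seen outside OptumCare, on EMR review. A control admission missing from those sources is a 0 as well. Participants also have daily wellness checks and clinical outreach, which controls lack, and the Protocol (6.5.2) plans a later claims check on consistency. These points stand, and step 5 shows that they can cancel or reverse the bias.

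Finally, the group may be small. A participant is unconfirmed only if claims, EMR and infusion pharmacy data all fail, which should be uncommon among UHC members. Whether the analysis is confined to UHC members is where 5.1.1 and 5.8.1.2 disagree.

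**Conclusion.** The point holds as a gap with a biased default. The plan identifies participants with unknown outcome, gives early discontinuation a rule only in the time-to-event analysis, and for the binary primary endpoint has wording under which no observed admission means 0. The bias is likely toward the drug when control capture is good, but neither its direction nor its size is fixed by the documents.

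Under no drug effect, a 15% rate, complete control capture and equal risk, the chance of a false pro-drug result at 1,000 pairs is about 4%, 7%, 16% and 50% for 2%, 5%, 10% and 20% unconfirmed. At 2% the effect is slight; at 10% or more it would undermine the primary test. The unconfirmed shares are my assumption. The stronger readings, that the SAP expressly codes these participants as successes or that the error runs in one direction only, should not be drawn.

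**What to change.** Before outcome data are accessed, amend SAP 4.5 and 5.8.3 as follows.

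1. Apply one data-coverage requirement to both groups: from the index date through Day 28 or death. State the index date once, because 4.5 defines the window from infusion but counts from diagnosis in its example.
2. Code the binary outcome as missing, not 0, when coverage is not confirmed and no admission is recorded. A recorded admission counts as an event whatever the coverage.
3. Make complete pairs the primary analysis, and report the number unconfirmed in each group.
4. Because loss may be informative and dropping pairs does not cure that (step 6), add sensitivity analyses: imputation at the control rate, and a worst-case or tipping-point analysis.
5. Reconcile 5.1.1 (UHC members only) with 5.8.1.2 (UHC and non-UHC), since this largely decides how many participants are unconfirmed.

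The cost is SAP text and some lost pairs. Even with 20% of 1,000 pairs lost, power for 15% versus 10% is about 0.86, above the 0.8 that SAP 4.4.2 asks for.
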